Participants will then use the study pump with Control-IQ technology 2.0 for 4 weeks during the study period (2 weeks with a lower target of 90-130 mg/dL, and 2 weeks with a standard target of 112.5-160 mg/dL, in random order). Participants will have a follow up contact at 1

day, 3 days and 1 week into Control-IQ 2.0 use, a follow-up visit at 2 weeks to switch targets, a follow up contact 3 days later and 1 week after switching targets, and a follow up visit at 4 weeks to end the study.

Participants will use the t:slim X2 insulin pump with Control-IQ technology 2.0 turned on. It is acceptable to use manual mode when there is a loss of CGM data.

Each participant will perform 2 late bolus meal challenges in each two-week period, contacting the study clinical site before and after each challenge.

An assessment of adverse events, using open ended questions to capture hyperglycemic and hypoglycemic events, and their underlying cause and relationship to the study device or other parts of the system (such as the infusion set), will occur at all visits/contacts.

Study Safety Plan:

Participants will be given a blood glucose and ketone meter to use throughout the study, and will be trained on their use by qualified staff.

[figure not shown]
BGM readings will be performed in accordance with the participant instruction sheet and per CGM manufacturer instructions.

Ketone readings will be performed per the participant instruction sheet.

Site investigators may adjust insulin delivery profile settings as needed throughout the study in accordance with their clinical practice.

Real-time CGM alerts will be sent to study staff providers (MD, DO, NP, PA) for the first ten 6-13 year old participants to begin use of the lower target (90-130 mg/dL) for the first week of Control-IQ 2.0 use at that target. In addition, real-time CGM alerts will be sent to study staff providers for all 2-5 year old participants throughout their use of Control-IQ 2.0 technology (all 4 weeks).

SCHEMATIC OF STUDY DESIGN

SCHEDULE OF STUDY VISITS AND PROCEDURES

Visit Number	1	2	3	4	5	6	7	8	9	10	11	12	13	14	UV
		R	un-In Po	eriod						Treatmo	ent Perio	d			
	Screening Visit	Control-IQ 1.5 Training Visit	Contr	ol-IQ 1.5 Period		Control- IQ 2.0 Training	Con		2.0 Tre riod 1	atment	Con	trol-IQ 2 Per	2.0 Trea iod 2	tment	
		Up to 2 weeks after screening	1d	3d	1w	2w	1d	3d	1w	2w	1d	3d	1w	2w (Final Visit)	UV

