3.3 Visit 6: Control-IQ 2.0 Training Visit

- After participants complete the run-in, they will return for the Control-IQ 2.0 training visit, and switch to
- the Control-IQ 2.0 study pump after training by qualified staff.
- Control-IQ 2.0 allow for selection of different glycemic targets, as well as toggling autoboluses in
- standard and exercise activity. The late bolus feature will also be available.
- Participants will be randomized to use either a daytime 30-min predictive glucose target of 90-130 mg/dL
- or 112.5 to 160 mg/dL for the first two-week period, then switch to the other target after 2 weeks.
- In the training visit, participants will:

327

328

329

332

337

345

346

347

348

349

350

351

352

353

354

355356

357

358

- 1) Select the appropriate target in clinic on their study pump per the randomization, and will be instructed by study staff to use the assigned glycemic target during each two week period.
 - 2) Be instructed that autoboluses will default to on during normal activity, and off during exercise activity.
 - 3) Be reminded again that use of the security PIN on the insulin pump will be required for anyone who is not entirely responsible for their own diabetes care, to include all 2-5 year olds, and those 6 years of age or older who may be only partially responsible for their own diabetes management.
 - 4) Be instructed that sleep activity will be required during Control-IQ 2.0 use. A sleep schedule should be programmed into the pump for use each night. Participants will be instructed to disable sleep or adjust the schedule on the nights of the late bolus meal challenges, then re-enable sleep activity as soon as the challenges are over, so it is used the rest of the night.
 - 5) Review prior training guidelines from the Control-IQ technology 1.5 training visit, and be taught how the new features are different in Control-IQ technology 2.0.
 - 6) Review the study meal late bolus challenges, to be performed twice in each two week period. Participants may also use late bolus as desired outside of the challenges.
- The participant will be given a User Guide as a reference as well as review the Hypoglycemia and
- Hyperglycemia Treatment Guidelines as part of the Study Participant Instruction Sheet. The study device
- training form will be completed.
- Participants will be instructed to download the study device prior to each phone contact or office visit.

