3.4.1 Procedures at all Study Visits

- 400 The following procedures will be performed at each visit, unless otherwise specified:
- Review of study device data
- Assessment of compliance with study device use by review of any available device data
- Assessment of device issues that have occurred
- Assessment of adverse events, using open ended questions to capture hyperglycemic and
 hypoglycemic events, and their underlying cause and relationship to the study device or other parts of
 the system (such as the infusion set).
- Review of ongoing study late bolus meal challenges when in the treatment period
- Baseline INSPIRE questionnaire for pediatric participants age 8-17, for adult participants age 18+, and for parents of pediatric participants age 2-17 will be completed at visit 6
- Post Assessment INSPIRE questionnaire for pediatric participants age 8-17, for adult participants age 18+, and for parents of pediatric participants age 2-17 will be completed at visits 10 and 14
- SUS Scale will be completed at visits 10 and 14
- Study Specific Questionnaire will be completed at visits 10 and 14
- At the final visit (or at subject withdrawal), the study staff will then supervise the participants transition back to their standard of care therapy as follows:
 - Study staff will re-evaluate the subject's baseline therapy doses, noting changes in basal rates, carbohydrate ratios, and correction factors in use at the end of the trial. For prior CSII users, the study investigator will supervise and confirm the entry of settings in the insulin delivery profile of the participant's home pump at the end of the study.
 - For those subjects using basal insulin, doses will be adjusted to best match the current daily insulin requirements from CSII use, typically = (total daily dose + 20%)/2, with further modification as per clinical site usual practice.
- Participants must have two CGM or fingerstick BG values, separated by at least 15 minutes, that must be above 80 mg/dL prior to discharge from the clinic for the final visit. In addition, CGM trend arrow must not be going down at the time of discharge.

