- Study staff will confirm subjects have carbohydrates on hand for their drive back home, and instruct subjects to check their glucose levels when they arrive at home, prior to bedtime, and at least one time overnight on the first night to monitor for hypoglycemia, reminding subjects that insulin on board can be active for the next few hours even after stopping their pump.

430	3.5 Unscheduled Visits
431 432	Participants may have unscheduled visits during the study period if required for additional device training or other unanticipated needs per the study investigator discretion.
433	3.6 Late Bolus Meal Challenges
434 435	Participants will complete two late bolus meal challenges during each two week treatment period. Procedures are described in section 5.1.
436	3.7 Adjustments in Insulin Pump Settings
437 438 439	Insulin and glucose data from the screening visit, as well as follow up visits, will be reviewed and the site investigator may adjust insulin delivery profile settings as needed in accordance with their clinical practice.
440	3.8 Early Discontinuation of Study Device
441 442 443 444 445	If the participant cannot be reached for scheduled study contacts, the participant's other contact methods will be utilized. Participants who are not compliant with the arranged contacts on two separate occasions may be discontinued at the discretion of the investigator. Participants who discontinue the study device prior to the final visit, either by choice or by investigator decision, will be asked to come for an end of study visit and then will be dropped from the study.
446	3.9 Remote Monitoring
447 448 449 450	Real-time CGM alerts will be sent to study staff providers (MD, DO, NP, PA) for the first ten 6-13 year old participants to begin use of the lower target (90-130 mg/dL) for the first week of Control-IQ 2.0 use at that target. This requirement will only be removed for future participants in this age group after the first ten participants finish the first week of use of the lower target, and no safety concerns arise, where:
451 452 453	 No severe hypoglycemia events related to algorithm delivered automated insulin dosing occur that required study staff intervention because the participant was not aware/treating appropriately.
454 455 456	 No severe hyperglycemic events related to algorithm delivered automated insulin dosing occurred that required study staff intervention because the participant was not aware/treating appropriately.

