491 492 493	A paper logbook will be provided to participants that includes a page to record details about each challenge and procedural instructions about how participants will conduct these challenges. This material will be reviewed with each participant, and will be used for source verification for the eCRF database.
494 495 496 497 498	Before starting each challenge, participants (or parent/guardian if the participant is < 18 years of age) must assure the participant has a working CGM and Control-IQ is active. For pediatric participants, the participant's parent or guardian must remain with the child at all times and monitor CGM readings frequently during and through meal completion plus 5 hours (3 hours for participants age 2-5). Snacks and glucagon must be available for use during and after each challenge.
499 500 501 502	Participants will be instructed to communicate with study staff within one day prior to each challenge to review procedures and to have a contact with study staff no more than 1 day after the completion of each challenge. The participant or parent/guardian must have an on-call phone number for the study team prior to initiation of each challenge.
503 504	Hyperglycemia and Hypoglycemia treatment guidelines (sections 3.1.3 and 3.1.2) remain in effect for the challenges, and will be reviewed with participants prior to each challenge.
505 506	Site staff will directly contact the participant if they do not receive a follow up contact from participants when 24 hours have passed since the time of completion of the planned challenge.
507	5.1.1 Late Bolus Meal Challenges
508 509	All challenges will be performed with the last meal of the day (dinner) and participants will be instructed not to snack after dinner on days they are performing meal challenges, unless it is to treat hypoglycemia.
510 511 512	Participants will also be instructed not to use sleep activity for at least 5 hours (3 hours for participants age 2-5) once starting the meal challenge. Participants will be reminded to disable sleep activity if it is inadvertently activated during the challenge, and to re-enable it at the end of the challenge.
513	Time zero (start of the challenge) is at the first bite of food for the study meal.
514 515	During each two week treatment period with Control-IQ technology 2.0 use, the two meal challenges will consist of:

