516 517 518	 Full bolus for the given carbohydrates and calculated correction, given 45 minutes after starting the meal, based on calculated bolus dose using the bolus calculator (with full amount of carbohydrates entered).
519 520 521	• Full bolus for the given carbohydrates and calculated correction, given 45 minutes after starting the meal, based on calculated bolus dose using the bolus calculator (with full amount of carbohydrates entered) AND enabling the late bolus feature to 45 minutes later.
522	For each meal challenge, participants will:
523 524	1. Be in a fasting state for two hours prior to consuming the last meal of the day, with the last manual insulin bolus more than two hours prior to the meal.

- 525 2. For participants age 6+, only begin the meal challenge if CGM glucose is between 70 mg/dL and 200 mg/dL, and CGM trend arrow is not down.
- For participants age 2-5, only begin the meal challenge if CGM glucose is between 70 mg/dL and 250 mg/dL, and CGM trend arrow is not down.
- 529 Subjects with hyperglycemia > 200mg/dL will reschedule their challenge for another time. If < 530 To mg/dL, carbohydrate treatment can be given, after which the meal challenge can continue.
 - 3. Pediatric participants age 2-5 should have a meal with at least 20 grams of carbohydrates. Participants age 6-13 should have a meal with at least 35 grams of carbohydrates. All other participants should have at least 50 grams of carbohydrates for the study meal challenges. *Each participant should use the same meal for all of their meal challenges in the study. Participants will be encouraged to use the same frozen entrée of their choice for consistency.*
 - 4. Do their best to complete the meal within 30 minutes of starting to eat.
 - 5. Write down the start and end time of eating the meal, as well as the meal content (to include amount of carbohydrate, protein and fat) on the study provided logbook.
 - 6. Bolus for the meal 45 minutes after starting to eat, entering the full carbohydrate amount and using the recommended dose from the bolus calculator. For one of the two challenges during a single treatment period, use the bolus calculator but do not change the bolus time. For the other challenge during the same treatment period, use the bolus calculator but change the bolus time to 45 minutes late.

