2. CGM hypoglycemia outcomes, compared between the three study time periods 922 a. Overall % time <54 mg/dL 923 b. Overall % time <70 mg/dL 924 3. Times in ranges-overall (70-180 mg/dL, >180 mg/dL, >250 mg/dL, 70-140 mg/dL) compared 925 between the three study time periods 926 4. Mean glucose compared between the three study time periods. 927 5. Overall variability (CV and SD) compared between the three study time periods 928 6. Secondary endpoints 2 - 5 compared during daytime and nighttime, across the three study time 929 930 periods 7. Secondary endpoints 2 - 5 as well as adverse events, during the study meal challenge periods, for 931 late bolus feature use compared to normal bolus in the meal challenges. 932 8. Time to intervention for hypo- or hyperglycemia during the study meal challenge periods, for late 933 bolus feature use compared to normal bolus in the meal challenges. 934 935 9. Number of interventions for hypo- or hyperglycemia during the study meal challenge periods for late bolus feature use compared to normal bolus in the meal challenges. 936 10. Subgroup Analysis for all metrics by age cohort, baseline HbA1c cohort (HbA1c at baseline of > 937 7.5%, yes/no), and target activity use (standard target, lower target, sleep activity, exercise 938 939 activity). 940 8.5 Analysis Datasets 941 942 Safety analysis set: All participants who initiate the Treatment Period and use the study device at least one time (including training). 943 CGM analysis set: Any member of the Safety Analysis Set who has at least 24 hours of CGM data during 944 945 either Treatment Period. CGM data occurring within the meal challenge windows (from time of start of meal up to 5 hours afterwards [3 hours for age 2-5]) will not be used to determine whether a subject is 946 included in CGM analysis set or not. 947 948 Late bolus meal challenge set: Any member of the Safety Analysis Set who has at least 24 hours of CGM data during the Treatment Period, and who has at least 3 hours of CGM data for at least one meal 949 challenge. 950 8.6 Analysis of Endpoints 951 8.6.1 Analysis of the Safety Event Endpoints 952 953

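### Autobolus state and pump settings may differ between the two meal challenges being compared, challenge order is left open, and section 8.6.4 uses neither

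*Combined protocol and SAP*

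**What the plan says.** **The comparison.** Secondary endpoints 7 to 9 (synopsis and section 8.4) cover CGM outcomes and adverse events, time to intervention, and number of interventions, each for "late bolus feature use compared to normal bolus in the meal challenges". Section 5.1.1 puts one challenge of each kind in every treatment period. In both, the bolus is given 45 minutes after the meal starts, "based on calculated bolus dose using the bolus calculator (with full amount of carbohydrates entered"). The intended difference is whether the participant also tells the pump that the bolus is 45 minutes late.

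**Autoboluses.** Section 3.3 states "Control-IQ 2.0 allow for selection of different glycemic targets, as well as toggling autoboluses in" standard and exercise activity. The matching training step is "Be instructed that autoboluses will default to on during normal activity, and off during exercise activity". That is a default; the section does not ask for the state to be kept constant.

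**Profile settings.** Under section 3.7, after review of screening and follow-up data, "the site investigator may adjust insulin delivery profile settings as needed in accordance with their clinical practice". The synopsis, under the safety plan, is wider: "Site investigators may adjust insulin delivery profile settings as needed throughout the study in accordance with their clinical practice". Section 3.4.1 shows what such settings include: at the final visit staff note changes in basal rates, "carbohydrate ratios, and correction factors in use at the end of the trial".

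**Checks before a challenge.** Section 5.1 says that the participant or parent "must assure the participant has a working CGM and Control-IQ is active". Section 3.3 has staff verify the glycemic target at each contact. Neither mentions autobolus state or profile settings.

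**Analysis.** Section 8.6.4.1 reduces CGM outcomes to the mean of the two challenges in a period, one value per participant per period. Section 8.6.4.2 compares the two targets on time to intervention. Section 8.6.4.3 summarises interventions by and across treatment periods. None of them uses pump settings or challenge order.

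**The concern.** A within-person comparison of two meals is informative only if the meals differ in the feature under test and otherwise differ at random. The protocol clearly aims at this: same meal, fasting beforehand, a starting glucose range, fixed bolus timing, no exercise, sleep activity off. Two things that bear directly on insulin delivery are left free, and the schedule lets the result of the first challenge influence them before the second.

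Suppose the first challenge ends in a low and a setting is then changed for good clinical reasons. The second challenge differs from the first both in the late bolus feature and in that setting. If most participants take the two challenges in the same order, these changes line up with the feature and shift the contrast. If order is even, they mainly add scatter. The hypoglycemia and intervention results for the feature are the most exposed, because lows and highs are what prompt a change.

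**Working it through.** The plan gives no effect size, standard deviation or power figure for the challenges, so there is nothing to reproduce. The check is a reading of the rules, followed by an illustration on assumed inputs.

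**1. What is held constant between the two challenges of a period**

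| Item | Held the same? | Where |
|---|---|---|
| Meal, fasting, starting glucose range | Yes | 5.1.1 |
| Bolus timing and use of the calculator's dose | Yes | 5.1.1 |
| Physical exercise, sleep activity | Yes, both excluded | 5.1.1 |
| CGM working, Control-IQ active | Yes | 5.1 |
| Glycemic target | Yes, same within a period | 3.3 |
| Autobolus state | Default only | 3.3 |
| Carbohydrate ratio, correction factor, basal rates | No rule | 3.7, synopsis |
| Which challenge comes first | No rule | 5.1.1 |

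**2. Can the first result reach the second challenge?** Section 5.1 requires at least 48 hours between challenges and a staff contact no more than 1 day after each. With a 5-hour window that contact falls at the latest 5 + 24 = 29 hours after the meal starts. Counting the 48 hours from start to start, at least 48 − 29 = 19 hours remain. At age 2-5 the figures are 3 + 24 = 27 and 21 hours. A further contact is due within a day before the second challenge. So the opportunity exists in every pair; how often it is used is unknown.

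**3. Effect on the dose (assumed changes).** The carbohydrate part of the bolus is grams divided by the ratio in grams per unit. Lowering the ratio by a share c multiplies it by 1/(1 − c). For c = 5%, 10% and 20% the same meal draws 5.3%, 11.1% and 25.0% more insulin. Raising the ratio acts the other way.

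**4. Effect on the contrast.** At least 72 completers give 72 × 4 = 288 challenges, or 72 × 2 = 144 within-period pairs. Let
- f = share of pairs with a setting changed between the challenges,
- d = effect of that change on the second challenge's outcome, in SD of the participant's late-minus-normal difference,
- q = share of pairs with the late-bolus challenge second.

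The difference gains d when late bolus is second and loses d when it is first, so

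bias = f × d × (2q − 1).

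With one difference per participant, n = 72 and a two-sided 5% level (8.16), a normal approximation gives the chance of a nominally significant result when the feature does nothing: Φ(−1.96 + bias × √72) + Φ(−1.96 − bias × √72), where √72 = 8.485. With d = 0.5 (assumed):

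| f | q = 0.5 | q = 0.75 | q = 1 |
|---|---|---|---|
| 10% | 0 SD; 5.0% | 0.025 SD; 5.5% | 0.05 SD; 7.1% |
| 25% | 0 SD; 5.0% | 0.0625 SD; 8.3% | 0.125 SD; 18.6% |
| 50% | 0 SD; 5.0% | 0.125 SD; 18.6% | 0.25 SD; 56.4% |

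**5. The noise when order is balanced.** Added variance is f × d². At f = 25%, d = 0.5 it is 0.25 × 0.25 = 0.0625. With the SD otherwise 1, the SD becomes √1.0625 = 1.03, about 3% wider.

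**6. What accounting for order does.** With true effect τ, late-second pairs average τ + fd and late-first pairs τ − fd. The equal-weight mean of the two is τ whatever q is. This holds if f × d is the same in both orders. If the kind of challenge taken first affects how often or how far settings change, half the difference between the two products remains, even with randomised order.

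**7. What 8.6.4.1 does.** Averaging late and normal within a period cancels the late-minus-normal difference. As written, the CGM part of endpoint 7 has no contrast to report.

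**The case against.** Several points on the other side stand.

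- **Toggling is a capability, not an invitation.** A reader might infer that participants are expected to switch autoboluses around challenges. Section 3.3 does not say that: it describes the device and teaches a default of on in normal activity. How often anyone toggles is unknown.
- **Section 3.7 ties adjustment to data review,** and section 5.1 does not call for a settings change at the post-challenge contact. The wider permission comes from the synopsis.
- **Some instructions are not in the documents.** The participant instruction sheet and the logbook's procedural text could address settings.
- **A bias in mg/dL is tempting but unsupported.** One could assume 50 g at 1 U per 10 g, raise the ratio to 11 g per U (50/10 − 50/11 = 0.45 U), and multiply by an assumed 50 mg/dL per U to get about 23 mg/dL. None of these inputs except the 50 g minimum is in the documents. The conversion also ignores automated delivery, which must be active in a challenge and would offset part of the difference, and treats a full insulin effect as a shift in a 5-hour or 3-hour mean. Changes in opposite directions would partly cancel.
- **Restricting to pairs with identical settings looks like a cure and is not.** If settings change because the first challenge went low or high, that restriction drops pairs on the first challenge's outcome and can create its own bias.
- **The endpoints are exploratory.** Section 8.2 disclaims formal inference.

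The assumption in section 8.1 of no period or carryover effects does not answer the point. It is stated for the crossover design and does not address the order of two challenges inside one period.

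**Conclusion.** The gap is real and modest. Autobolus state and profile settings may differ between the two challenges that endpoints 7 to 9 compare, their order is left open, and section 8.6.4 neither looks at these things nor, for CGM outcomes, keeps the two challenges apart. The consequence is added noise, or bias if order is unbalanced and changes follow the first result.

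Its size cannot be derived from the documents. In the simple model the average bias is zero with balanced order, and the cost is then a slightly wider interval. The larger figures in the table need both frequent changes and a strongly one-sided order, neither of which the documents indicate. All of them rest on assumed f, d and q, and on f × d being alike in both orders.

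A reader might go further and conclude that the late-bolus results will be biased, or that settings ought to be frozen during challenges. The documents support neither. They establish that differing settings are possible, not that they are common, and whether settings may change is a clinical matter. This is a cheap improvement to an exploratory analysis, not a threat to the primary safety endpoints.

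**What to change.** Leave the clinical freedom to adjust settings as it is, and then:

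1. **Reconcile the sections.** The sponsor should state how the standardisation rules in 5.1 and 5.1.1 fit with toggling and adjustment under 3.3, 3.7 and the synopsis. What that rule should be is for the sponsor.
2. **Order.** Randomise which challenge comes first in each treatment period or, failing that, record it.
3. **Settings as data.** For each challenge, take autobolus state, carbohydrate ratio, correction factor and delivered insulin from the uploaded pump data. Confirm first that the files hold these items with dates; if one is missing, add a line to the challenge logbook.
4. **Main challenge analysis.** In 8.6.4, make the paired late-minus-normal contrast over all pairs, with challenge order accounted for, the main analysis for endpoints 7 to 9. The within-period average can stay as a separate summary for comparing targets.
5. **Discordant pairs.** Report how many pairs have differing settings, by order and by direction of change. Show the identical-settings subset as descriptive only, with a note that it is selected partly on the first challenge's result.

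The cost is a short randomisation list or one recorded field, some extraction from files already collected, and slightly more analysis work. The subset will be smaller than the full set and cannot carry the conclusion.
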